11.1.1. Percentage of responders at Post-Baseline Visits

A subject is defined as a responder if they have a $\geq 30\%$ (and $\geq 50\%$) improvement in ADHD RS-IV HV total score compared with the DB baseline.

A similar definition for responder will be defined if the subject has a $\geq 30\%$ (and $\geq 50\%$) improvement in ADHD RS-IV HV total score compared with the OL baseline.

The number of subjects with such responses compared to DB baseline and OL baseline will be summarized by DB treatment and overall, and by visit for the ITT population.

11.2. CHANGE IN CGI-S

The CGI-S modified assessment asks the clinician one question: “Considering your total clinical experience with this population, how mentally ill is the subject at this time?” The clinician’s answer is rated on the following 7-point scale: 1 = normal, not at all ill; 2 = borderline mentally ill; 3 = mildly ill; 4 = moderately ill; 5 = markedly ill; 6 = severely ill; 7 = among the most extremely ill subjects.

The analysis will be performed using the same methodology described above for the ADHD RS-IV endpoint, using the ITT population.

The line-plot of Mean (\pm SE) change from DB baseline and OL baseline in CGI-S score will be provided by DB treatment and overall, and by visit.

11.3. CHANGE FROM BASELINE IN THE ADHD RS-IV HV INATTENTIVENESS AND HYPERACTIVITY SCORES

For the hyperactivity-impulsivity and inattentiveness subscales of the ADHD RS-IV HV, the same methodology used for the ADHD RS-IV HV Total score described in [section 11.1](#) will be used.

11.4. CHANGE FROM BASELINE IN CONNERS 3-P SCALE SCORES

The Conners 3rd Edition - Parent (Conners 3-P) assesses behaviors and other concerns in children between the ages of 6 and 18, inclusive. The full-length version of the Conners 3-P will be used. Assessments of Conners 3-P are completed at each clinic assessment visit as well as assessment of the child's behavior over the past week prior to the parent's assessment. The full-length version provides a thorough assessment of ADHD and addresses comorbid disorders such as Oppositional defiant disorder (ODD) and conduct disorder. Responses to the Conners 3-P will be used to calculate the scale scores.

The item numbers associated with each scale are noted below.

Conners 3-P Content Scales

Inattention (10 items)

- 12. Has trouble staying focused on one thing at a time.
- 23. Has a short attention span.
- 28. Avoids or dislikes things that take a lot of effort and are not fun.
- 44. Has trouble concentrating.
- 47. Doesn't pay attention to details; makes careless mistakes.
- 49. Has trouble changing from one activity to another.
- 67. Inattentive, easily distracted.
- 77. Gets bored.
- 88. Gives up easily on difficult tasks.
- 95. Has trouble keeping his/her mind on work or play for long.

Hyperactivity/Impulsivity (14 items)

- 19. Fidgeting.
- 43. Blurts out answers before the question has been completed.
- 45. Is constantly moving.
- 50. Excitable, impulsive.
- 52. Gets over-stimulated.
- 54. Acts as if driven by a motor.
- 55. Blurts out the first thing that comes to mind.
- 61. Has difficulty waiting for his/her turn.
- 69. Runs or climbs when he/she is not supposed to.
- 71. Is noisy and loud when playing or using free time.
- 93. Leaves seat when he/she should stay seated.
- 98. Fidgets or squirms in seat.
- 99. Restless or overactive.
- 104. Interrupts others (for example, butts into conversations or games).

Learning Problems (9 items)

- 5. Spelling is poor.
- 7. Does not understand what he/she reads.
- 9. Is good at memorizing facts. (R)
- 15. Forgets things already learned.
- 36. Has trouble with reading.
- 51. Needs extra explanation of instructions.
- 53. Learns information as separate facts; does not “get the big picture.”
- 60. Reads slowly and with a lot of effort.
- 87. Cannot grasp arithmetic.

Executive Functioning (9 items)

- 34. Fails to finish things he/she starts.
- 37. Has trouble getting started on tasks or projects.
- 63. Completes projects at the last minute.
- 72. Is good at planning ahead. (R)
- 75. Forgets to turn in completed work.
- 79. Fails to complete schoolwork, chores, or tasks (even when he/she understands and is trying to cooperate).
- 84. Has trouble organizing tasks or activities.
- 90. Is messy or disorganized.
- 97. Loses things (for example, schoolwork, pencils, books, tools, or toys).

Defiance/Aggression (14 Items)

- 16. Bullies, threatens, or scares others.
- 22. Is cold-hearted and cruel.
- 27. Uses a weapon (for example, a bat, brick, broken bottle, knife, or gun).

- 30. Starts fights with others on purpose.
- 39. Physically hurts people.
- 46. Tells lies to hurt other people.
- 48. Is angry and resentful.
- 57. Tries to get even with people.
- 58. Steals secretly (for example, shoplifting or forgery).
- 65. Intentionally damages or destroys things that belong to others.
- 83. Threatens to hurt others.
- 86. Swears or uses bad language.
- 94. Actively refuses to do what adults tell him/her to do.
- 102. Argues with adults.

Peer Relations (6 Items)

- 10. Does not get invited to play or go out with others.
- 13. Has no friends.
- 24. Has trouble keeping friends.
- 62. Is one of the last to be picked for teams or games.
- 64. Interacts well with other children. (R)
- 92. Does not know how to make friends.

DSM-IV-TR Symptom Scales ADHD Inattentive (10 Items)

- 2. Is forgetful in daily activities.
- 28. Avoids or dislikes things that take a lot of effort and are not fun.
- 35. Does not seem to listen to what is being said to him/her.
- 47. Doesn't pay attention to details; makes careless mistakes.
- 68. Does not follow through on instructions (even when he/she understands and is trying to cooperate).
- 79. Fails to complete schoolwork, chores, or tasks (even when he/she understands and is trying to cooperate).
- 84. Has trouble organizing tasks or activities.
- 95. Has trouble keeping his/her mind on work or play for long.
- 97. Loses things (for example, schoolwork, pencils, books, tools, or toys).
- 101. Is easily distracted by sights or sounds.

ADHD Hyperactive-Impulsive (11 items)

- 3. Talks too much.
- 45. Is constantly moving.
- 54. Acts as if driven by a motor.
- 69. Runs or climbs when he/she is not supposed to.
- 43. Blurts out answers before the question has been completed.
- 61. Has difficulty waiting for his/her turn.

- 71. Is noisy and loud when playing or using free time.
- 93. Leaves seat when he/she should stay seated.
- 98. Fidgets or squirms in seat.
- 99. Restless or overactive.
- 104. Interrupts others (for example, butts into conversations or games).

Conduct Disorder (15 items)

- 6. Skips classes.
- 11. Has forced someone into sexual activity.
- 16. Bullies, threatens, or scares others.
- 27. Uses a weapon (for example, a bat, brick, broken bottle, knife, or gun).
- 30. Starts fights with others on purpose.
- 39. Physically hurts people.
- 41. Is cruel to animals.
- 56. Lies to avoid having to do something or to get things.
- 58. Steals secretly (for example, shoplifting or forgery).
- 65. Intentionally damages or destroys things that belong to others.
- 76. Runs away from home for at least one night.
- 78. Has intentionally set fires for the purpose of causing damage.
- 89. Has broken into someone else's house, building, or car.
- 91. Goes out at night even though it breaks the rules.
- 96. Steals while confronting a person (for example, mugging, purse snatching, or armed robbery).

Oppositional Defiant Disorder (8 items)

- 14. Loses temper.
- 21. Blames others for his/her mistakes or misbehavior.
- 48. Is angry and resentful.
- 57. Tries to get even with people.
- 59. Annoys other people on purpose.
- 73. Is irritable and easily annoyed by others.
- 94. Actively refuses to do what adults tell him/her to do.
- 102. Argues with adults.

Indices

Conners 3-P ADHD Index (10 Items)

- 19. Fidgeting.
- 35. Does not seem to listen to what is being said to him/her.
- 47. Doesn't pay attention to details; makes careless mistakes.
- 67. Inattentive, easily distracted.
- 84. Has trouble organizing tasks or activities.

- 88. Gives up easily on difficult tasks.
- 98. Fidgets or squirms in seat.
- 99. Restless or overactive.
- 101. Is easily distracted by sights or sounds.
- 104. Interrupts others (for example, butts into conversations or games).

Conners 3-P Global Index (10 Items)

- 19. Fidgeting.
- 25. Cries often and easily.
- 29. Mood changes quickly and drastically.
- 34. Fails to finish things he/she starts.
- 40. Demands must be met immediately—easily frustrated.
- 50. Excitable, impulsive.
- 67. Inattentive, easily distracted.
- 81. Temper outbursts.
- 85. Disturbs other children.
- 99. Restless or overactive.

Each item has responses provided as 0 = Not true at all (Never, Seldom), 1 = Just a little true (Occasionally), 2 = Pretty much true (Often, Quite a bit), 3 = Very much true (Very often, Very frequently).

Items marked with a (R) are reverse scored. The responses will be scored as (4 - item score) when contributing to a raw score.

For each scale except the ADHD Index, raw scores for each scale are calculated as the sum of the item responses (taking into account any reverse scored items).

For the ADHD Index, the item responses are transposed prior to calculating the sum. For item numbers 19, 47, 67, 84, 99, 101, and 104, the following transposition is made. If the item response is 0 or 1, then the transposed score = 0. If the item response is 2 then the transposed score = 1. If the item response is 3 then the transposed score = 2.

For the item numbers 35, 88, and 98, the following transposition is made. If the item response is 0 or 1, then the transposed score = 0. If the item response is 2 or 3, then the transposed score = 2.

In the event of a missing item response, Conners gives the following guidance as to the maximum number of allowable item omissions.

Scale	Total Items	Maximum Allowable Item Omissions
Inattention	10	1
Hyperactivity/Impulsivity	14	2

Scale	Total Items	Maximum Allowable Item Omissions
Learning Problems	9	1
Executive Functioning	9	1
Defiance/Aggression	14	2
Peer Relations	6	1
DSM-IV-TR ADHD Inattentive	10	1
DSM-IV-TR ADHD Hyperactive-Impulsive	11	2
DSM IV-TR Conduct Disorder	15	2
DSM IV-TR Oppositional Defiant Disorder	8	1
Conners 3 ADHD Index	10	1
Conners 3 Global Index	10	1

If there are omitted item responses and the number of omitted item response does not exceed the maximum allowable item omissions, then the raw score will be prorated as:

Prorated Score = (Obtained raw score for scale / Total number of items in scale with a response) * (Total number of Items in the scale). As an example, if the Hyperactivity/Impulsivity has responses for 12 of the 14 items in the scale, then the number of missing responses is less than or equal to the maximum allowable number of omissions. Suppose the sum of the responses provided is 15. Then the prorated score will equal $(15/12) * 14 = 17.5$.

If the number of omitted item responses exceeds the maximum allowable number noted, the raw scale score will not be calculated.

For all scale scores except the ADHD Index, the raw scores will be converted to age/sex adjusted T-scores according to the scoring manual (Conner, 2008). The T-scores will be used in the statistical analyses.

For the ADHD Index score, the total of the transposed scores (or prorated transposed score, if 1 item response is missing) is given a probability index score according to the following table. The probability score is the probability of a classification of ADHD based on the total transposed score.

Total Transposed Score	Probability (%)
0	11
1	29
2	41
3	51
4	56
5	64

Total Transposed Score	Probability (%)
6	71
7	77
8	82
9	87
10	91
11	94
12	97
13	98
14	99
15	99
16	99
17	99
18	99
19	99
20	99

The probability score for the ADHD Index will be used in the statistical analysis.

For the Conners 3-P scale scores, the same methodology, described for the ADHD RS-IV Total in [section 11.1](#), will be used for this analysis. The analysis will be performed using the ITT population.

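### SAP 11.4 reverses Conners 3-P items as 4 − item although items run 0 to 3, so three scales are 1 raw point too high on complete forms; separately, some listed Conners endpoint scores have no scoring or mapping rule

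*SAP*

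**What the plan says.** SAP 11.4 gives one response key for all Conners 3-P items. It starts at 0 and ends with "2 = Pretty much true (Often, Quite a bit), 3 = Very much true (Very often, Very frequently". For the items marked as reversed, the rule is "The responses will be scored as (4 - item score) when contributing to a raw score".

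Three items carry the reversal mark: "9. Is good at memorizing facts. (R" in Learning Problems, "72. Is good at planning ahead. (R" in Executive Functioning and "64. Interacts well with other children. (R" in Peer Relations (each followed in the SAP by a closing bracket). None of them appears in any other listed scale.

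Except for the ADHD Index, a raw score is the sum of the items after reversal. If omissions stay within a stated limit (one item for each of these three scales), the raw score is divided by the number of items answered and multiplied by the number in the scale. Then "the raw scores will be converted to age/sex adjusted T-scores according to the scoring manual", and the T-scores are analysed. For the analysis, "For the Conners 3-P scale scores, the same methodology, described for the ADHD RS-IV Total in" section 11.1 applies. That section reports observed values as well as changes from the double-blind (DB) and open-label (OL) baselines. Under SAP 6.2.1 both baselines come from the core study.

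Protocol 6.2 and SAP 5.2 list the Conners endpoint as a total score plus four subscales: Oppositional, Cognitive problems, Hyperactivity and ADHD Index. SAP 11.4 defines twelve scales: six content scales, four DSM-IV-TR scales and two indices. It defines no total. On recall, Protocol 11.2.1 has the parent look back over a month, while SAP 11.4 says a week.

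**The concern.** On a 0-to-3 item the reversal that stays on the same scale is 3 − item. Subtracting from 4 produces a value of 4, which no item allows, and makes 0 unreachable. The SAP's own ADHD Index transposition handles only the responses 0, 1, 2 and 3, so the 0-to-3 key is not a slip.

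A program that follows the SAP exactly will therefore look up three scales in the norm table with a raw score that is too high. Observed T-scores on those scales would be wrong at every visit with a complete form. Changes would be wrong wherever the offset does not cancel.

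The separate gap is that the total, Cognitive problems, Hyperactivity and Oppositional endpoints cannot be produced from the SAP without a choice that it does not record.

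**Working it through.** **The plan's own figure.** The only worked number in SAP 11.4 is a prorated Hyperactivity/Impulsivity score of 17.5, from a sum of 15 on 12 of 14 items: (15/12) × 14 = 17.5. It reproduces. That scale has no reversed item, so the example does not test the reversal rule.

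**Reversal, item by item** (response key and rule from SAP 11.4):

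| Response x | 4 − x | 3 − x | Excess |
|---|---|---|---|
| 0 | 4 | 3 | 1 |
| 1 | 3 | 2 | 1 |
| 2 | 2 | 1 | 1 |
| 3 | 1 | 0 | 1 |

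The excess does not depend on the response.

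**Effect on each scale** (item counts from SAP 11.4, one reversed item each):

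| Scale | Items | Range with 3 − x | Range with 4 − x, complete form | Excess, complete form | Excess, one other item omitted | Excess, reversed item omitted |
|---|---|---|---|---|---|---|
| Learning Problems | 9 | 0–27 | 1–28 | 1 | 9/8 = 1.125 | 0 |
| Executive Functioning | 9 | 0–27 | 1–28 | 1 | 9/8 = 1.125 | 0 |
| Peer Relations | 6 | 0–18 | 1–19 | 1 | 6/5 = 1.2 | 0 |

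The complete-form maxima are 8 × 3 + 4 = 28 and 5 × 3 + 4 = 19. With one non-reversed item omitted, the highest prorated scores are (7 × 3 + 4)/8 × 9 = 28.125 and (4 × 3 + 4)/5 × 6 = 19.2. The other nine scales contain no reversed item and are unaffected.

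**False raw change between two visits** (excess at the later visit minus excess at baseline):

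- Same missing-item pattern at both visits: 0.
- Complete, then reversed item omitted: 0 − 1 = −1. The other way round: +1.
- Between complete and one other item omitted: ±0.125 (nine-item scales) or ±0.2 (six-item scale).
- Between one other item omitted and the reversed item omitted: ±1.125 or ±1.2.
- Assumption, not stated in the documents: if core-study baselines were scored with 3 − x and this study with 4 − x, every change on complete forms is 1 − 0 = +1, an apparent worsening.

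**T-score size.** The conversion table is not in the documents, so the error in T points cannot be computed. The offset cancels in T-score change only where the conversion is linear and uncapped over the scores concerned.

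**Endpoint list against scored scales.**

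- Total score: no rule in SAP 11.4.
- Cognitive problems: no scale of that name and no mapping.
- Hyperactivity: two candidates, Hyperactivity/Impulsivity (14 items) and DSM-IV-TR ADHD Hyperactive-Impulsive (11 items), sharing 10 items.
- Oppositional: two candidates, Oppositional Defiant Disorder (8 items) and Defiance/Aggression (14 items), sharing 4 items (48, 57, 94, 102).
- ADHD Index: listed by name and given its own scoring rule.

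**The case against.** The arithmetic is not in dispute; the objections are about weight.

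- **Small reach.** The three scales are not named endpoints, the plausible matches for Oppositional and Hyperactivity contain no reversed item, the endpoint is a change, and no inference is planned. All of this stands and limits the severity. It does not make the observed scores right.
- **Non-cancellation is not shown to be common.** SAP 6.2.1 says that questionnaire domain scores at core-study Week 6 may come from different dates because some forms were incomplete. That shows incomplete forms occur, not that patterns differ between visits on these scales. A score carried forward from an earlier complete form has the same +1 and cancels. This stands: the documents give no frequency, and the ±1.125 and ±1.2 figures are extremes.
- **The core-study scenario is conjecture.** Nothing says the core study used another rule. This also stands, so the scenario is kept only as a labelled assumption. The SAP still does not say how the carried-over scores were derived.
- **The mapping gap is partly overstated.** Only one scale has Oppositional in its name, Hyperactivity/Impulsivity is the closer label for Hyperactivity, all scored scales appear to be analysed, and the table shells are separate attachments. The second Oppositional candidate is indeed weak. The undefined total and Cognitive problems remain.

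**Conclusion.** The concern holds. As written, the SAP makes Learning Problems, Executive Functioning and Peer Relations exactly 1 raw point too high on every complete form. The excess is 1.125 or 1.2 with one other item prorated, and zero if the reversed item is the one omitted. This follows from the SAP alone.

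In raw change the error is nil when the missing-item pattern and the scoring rule are the same at both visits; otherwise it is as listed in the check. How often patterns differ, which rule scored the core-study baselines, and the size in T points cannot be established from the documents.

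The affected outputs are secondary and descriptive. The error reaches the listed Conners endpoint only if the undefined total or Cognitive problems draws on one of the three scales. It should be fixed because following the plan exactly gives wrong values. The endpoint mapping and the recall wording are lesser points that would not carry this one on their own.

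**What to change.** - In SAP 11.4, change the reversal to 3 − item score and check it against the scoring manual.
- State that the DB and OL baselines carried over from the core study are scored by the same rule, or re-derived from the item responses.
- Either define the total and Cognitive problems and name the SAP 11.4 scale used for Hyperactivity and for Oppositional, or align the endpoint list with the scales that SAP 11.4 scores.
- State one recall period in both documents, the one printed on the form in use.

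The reversal rule and a mapping table are SAP and programming edits before database lock and need no new data. Changing the protocol's endpoint or recall wording would need written approval from the sponsor and the IRB/IEC under Protocol 17.5.

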11.5. WEISS FUNCTIONAL IMPAIRMENT RATING SCALE - PARENT REPORT (WFIRS-P)

The WFIRS-P is an ADHD-specific instrument completed by the parent/legal guardian to evaluate domains of daily functioning that are likely to be impaired in ADHD. The WFIRS-P comprises 50 items used to provide measures of impairment in 6 domains (family, learning and school, life skills, child’s self-concept, social activities and risky activities) and overall (total score). The items relate to the period since the last visit and are scored using a 4-point Likert scale: 0 (never or not at all); 1 (sometimes or somewhat); 2 (often or much); or 3 (very often or very much). The instrument is completed at Week 0, Week 14, and Week 26 or ET.

The WFIRS-P domain scores for each patient were the mean of the items in each domain, or of all the items for total score, omitting items with a missing or ‘not applicable’ score. WFIRS-P domain or total scores were considered invalid if more than 30 % of the item scores used for calculation were missing or ‘not applicable’ (with the exception of one question relating to siblings, for which a score of ‘not applicable’ could contribute to the minimum number of items).

For the WFIRS-P total score and domain scores, the same methodology used for the ADHD RS-IV HV Total score described in [section 11.1](#) will be used for this analysis.

Frequency summaries of the count of items with a response of 2 or 3 will also be done by DB treatment group (and overall), and visit.

11.6. SUBGROUP ANALYSIS

Subgroup analyses of the ADHD RS-IV HV total score will be conducted using the following subsets of the ITT population:

- Gender: Male and Female
- Race Group: White, Black or African American, Asian, and Other
- DB Study Age Group (6-9 years, 10-12 years)
- DB Baseline Study BMI category: Underweight (< 5 percentile), Normal (≥ 5 - < 85 percentile), Overweight (≥ 85 - < 95 percentile), Obese (≥ 95 percentile)

12. SAFETY

The safety will be assessed on the basis of study agent exposure, adverse events, clinical laboratory data, ECG parameters, vital signs, physical examinations, neurological examinations, Tanner Staging, Children's Sleep Habit's Questionnaire (CSHQ), and Columbia - Suicide Severity Rating Scale (C-SSRS) Children's Assessment.

All safety data listings will be presented by subject and visit for all enrolled subjects.

The safety data summarizations will be performed in the safety population.

12.1. ADVERSE EVENTS (AEs)

The summary of AEs (or SAEs) will be limited to TEAEs. A TEAE is any AE (or SAE) occurring on or after the date of the first dose of study drug in the SEP360-310 study. All AEs will be coded using MedDRA version 19.0.

TEAEs will be further divided into:

- 1.) Those events with onset between the date of the first dose of study drug in the SEP360-310 study and 3 days after the last dose of study medication in SEP360-310, inclusive. These will be called on treatment events.
- 2.) Those events with onset more than 3 days after the last dose of study medication in SEP360-310. These will be called post-treatment events.

AEs with preferred terms of “Insomnia”, “Initial insomnia”, “Middle insomnia”, or “Terminal insomnia”, or AEs with Higher Level Term of “Disturbances in initiating and maintaining sleep” will be presented on AE tables in a combined term called “Combined insomnia” with the individual preferred terms within the combined term directly underneath.

All TEAEs will be summarized by SOC and PT. Though only TEAEs will be included in the summary tables, all AEs will be included on the listings (non-TEAEs will be flagged).

An overall summary table of TEAEs by DB treatment will be produced for the following categories:

- Number and percentage of subjects with a TEAE
- Number and percentage of subjects with a treatment-related TEAE
- Number and percentage of subjects with a TEAE leading to discontinuation
- Number and percentage of subjects with a Treatment-related TEAE leading to discontinuation
- Number and percentage of subjects with a serious TEAE
- Number and percentage of subjects with a serious TEAE leading to discontinuation
- Number and percentage of subjects with a treatment-related serious TEAE
- Number and percentage of subjects with a Treatment-related serious TEAE leading to discontinuation
- Number and percentage of subjects with a TEAE leading to death

This overall summary will be repeated for each onset period. For the post-treatment events, the denominators will be the number of subjects in each DB treatment group whose end of study visit was more than 3 days after the last dose date.

Subgroup analyses of the above noted TEAE categories will be produced for the following subgroups (sex, race (categorized as White, Black or African American, Asian, and Other), DB baseline age group (6-9 vs. 10-12 years)).

Adverse events will be summarized by DB treatment and overall for subjects in the safety population. The following summaries of AEs will be provided:

- TEAEs by SOC and PT
- TEAEs by PT
- TEAEs by PT ($\geq 3\%$ in any DB treatment group)
- Serious TEAEs by SOC and PT
- TEAEs leading to discontinuation by SOC and PT
- TEAEs by SOC and PT and maximum severity. Missing severity, if any, will be assumed as 'severe'.

- TEAE by relationship to study treatment (related or not related) by SOC and PT. Missing relationships, if any, will be assumed to be ‘related’.
- Treatment related SAEs by SOC and PT

The prevalence of Insomnia by study day in the study will be presented graphically by DB treatment and overall. Combined insomnia events will be used for this analysis. On any study day, the numerator will be the number of subjects who were experiencing insomnia (noting that subjects may have experienced multiple episodes during the study), and the denominator will be the number of subjects remaining on open-label study drug treatment.

The following listings of AEs will be provided:

- All AEs
- Adverse events leading to discontinuation of study drug
- Serious adverse events

In the summary tables subjects may be counted under multiple SOC and PTs, but for each SOC and PT, subjects are only counted once. If a subject has the same AE on multiple occasions, the highest severity (severe, moderate, mild) recorded for the event will be presented and the highest drug relationship (1 = ‘Unrelated’, 2 = ‘Unlikely to be Related’, 3 = ‘Possibly Related’, 4 = ‘Probably Related’, 5 = ‘Related’), reclassified into Related (‘Possibly Related’, ‘Probably Related’, ‘Related’) or Not Related (‘Unrelated’ and ‘Unlikely to be Related’), will be presented on the respective tables. Percentages are based on the number of subjects in the safety population.

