#### **12.4.1.** Serious Adverse Event

If the Investigator or study site staff becomes aware of SAE that occurs in a study subject from the time that informed consent/assent is signed through 30 days following the last dose of the study medication, this must be reported immediately to the Sponsor whether considered related or unrelated to the study drug. SAEs occurring from the time of informed consent to through 14 days following last dose of the study medication must be recorded on the CRF and the data recorded should match that on the SAE form.

Following the end of subject participation in the study, the Investigator or an authorized delegate should report SAEs "spontaneously" to PPD-PVG if considered at least possibly related to the study drug.

SAEs will be followed until resolution, loss to follow-up, stabilization of condition, or the event is otherwise explained.

In addition to the initial telephone notification, an initial SAE form as applicable must be completed and signed and sent via fax or email (see Table 1) to PPD-PVG within 1 business day of the Investigator or study site staff becoming aware of the event. The SAE report form must be signed by the Investigator or appropriate designee. The Sponsor provides the SAE form used to report SAEs.

The Sponsor or designee will promptly notify all study sites and Investigators of a SAE that is determined to be expedited to the Regulatory Authorities in accordance with applicable law(s) and regulation(s). These SAEs must be promptly reported to the Institutional Review Board (IRB) or Independent Ethics Committee (IEC) by the Principal Investigator or the appropriate person at the site.

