#### 15. STATISTICS

The Statistical Analysis Plan (SAP) will provide details on the statistical methods planned for this study and will be finalized before database lock (DBL).

All statistical summaries will be presented by treatment group from the double-blind core study as well as all subjects in the extension study.

Changes from baseline in safety and effectiveness endpoints will be calculated from both the double-blind (DB) baseline in the core study and the open-label (OL) baseline in the extension study, which is the Week 6 endpoint in the core study for most measures. No statistical inference will be performed for treatment comparison as this is a single arm, open-label, extension study.

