4.2. DETERMINATION OF SAMPLE SIZE

This study is projected to enroll up to 330 subjects based on the number of subjects who complete the core study.

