5. STUDY ENDPOINTS

5.1. PRIMARY ENDPOINT

The primary endpoint is:

- The incidence of overall AEs (or SAEs), and AEs (or SAEs) leading to discontinuation.

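### Post-treatment AE percentages in SAP 12.1 can count children who are not in their denominator, and no table by term separates on-drug from off-drug onset

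*SAP*

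**What the plan says.** The primary endpoint (SAP 5.1) is "The incidence of overall AEs (or SAEs), and AEs (or SAEs) leading to discontinuation". SAP 12.1 limits AE summaries to TEAEs and sets no upper time limit: "A TEAE is any AE (or SAE) occurring on or after the date of the first dose of study drug in the SEP360-310 study". The definition in Protocol 15.3.6.1 ends with a 2-week follow-up period.

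SAP 12.1 then divides TEAEs. Onsets from first dose to 3 days after last dose are on-treatment; later onsets are post-treatment. An overall table gives number and percentage in nine categories, including serious, related, leading to discontinuation and fatal. Of that table the SAP says "This overall summary will be repeated for each onset period". For the post-treatment version, "the denominators will be the number of subjects in each DB treatment group whose end of study visit was more than 3 days" after last dose. The on-treatment version has no special denominator.

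The remaining AE tables in SAP 12.1 (by SOC and PT, by PT, the 3% cut, serious, leading to discontinuation, maximum severity, relationship, related SAEs) are listed without a split by onset. For these, "Percentages are based on the number of subjects in the safety population".

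Under SAP 6.2.4, an early termination (ET) visit more than 3 days after last dose counts as EOS when EOS is missing.

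**The concern.** There are two separate faults.

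**Numerator and denominator.** Any treated child can have a post-treatment event, but only children with a qualifying EOS visit are in the denominator. If off-drug events reach the database by another route, the quotient need not be a proportion of the group named in the column. The route matters most for the gravest outcomes, because a child who dies after stopping drug cannot attend EOS.

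**Tables by term.** The SAP treats the on-drug/off-drug distinction as important enough to define, then applies it only to the overall summary. A reader of the SOC/PT tables cannot tell which terms arose on dasotraline and which after it was stopped. AE incidence is the primary endpoint and withdrawal a secondary objective, so this is information that the report would be expected to show.

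**Working it through.** No figure in the plan can be reproduced here. The study is descriptive ("No statistical inference will be performed for treatment comparison as this is a single arm, open-label, extension study") and the size is a projection ("This study is projected to enroll up to 330 subjects"). The check compares the rules first, then sizes their effect.

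**1. Can an off-drug event be recorded without a qualifying EOS visit?**
- Protocol 11.3.1 has AEs and SAEs monitored at all visits, including telephone assessments. Calls 11E and 12E precede EOS.
- Protocol 12.4.1 requires an SAE occurring "through 30 days following the last dose of the study medication, this must be reported immediately to the Sponsor", and requires CRF recording of SAEs through 14 days after last dose. EOS is 3 weeks ± 7 days after last dose (Protocol 7.1), so CRF recording does not depend on attending EOS.
- SAP 6.2.4 rescues only a late ET. A child whose ET was within 3 days of last dose and who has no EOS stays outside the denominator.

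So yes. The fatal-TEAE row is the clearest case: a child with a timely ET who dies more than 3 days after last dose and before EOS is a post-treatment event with no qualifying visit.

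**2. Size of the mismatch (assumed inputs).** The documents give neither EOS attendance nor post-treatment event rates. Take N = 330, a share f with a qualifying visit, 20 children with post-treatment events, and 5 of those 20 without the visit.

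| f | Denominator (330 × f) | As written, 20/denominator | Same set above and below, 15/denominator |
|---|---|---|---|
| 0.7 | 231 | 8.7% | 6.5% |
| 0.8 | 264 | 7.6% | 5.7% |
| 0.9 | 297 | 6.7% | 5.1% |

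If none of the 20 lacked the visit, the last two columns would agree.

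**3. Off-drug time in the pooled tables.** For a completer, last dose is Day 182, so the on-treatment window ends on Day 185. With EOS on Day 203, the post-treatment window is 203 − 185 = 18 days, and 18/203 = 8.9% of observed time. Over the protocol's EOS window, the range is 11/196 = 5.6% to 25/210 = 11.9%. For a child whose last dose is on Day 28, with EOS 21 days later on Day 49, it is 18/49 = 37%. Mixing is therefore small for completers and larger for early discontinuers.

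**4. Effect on one term (assumed rates, independent periods).** Pooled incidence = 1 − (1 − p_on)(1 − p_off). With 2% in each period, 1 − 0.98 × 0.98 = 3.96%. The term would enter the 3% table although neither period reaches 3%. With 5% on drug and 1% off drug, the table shows 1 − 0.95 × 0.99 = 5.95%.

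**The case against.** A reader might infer that neither on-drug nor off-drug incidence will be right, or that the primary endpoint is compromised. The documents do not support this. The overall summary for on-treatment onset uses the Safety population and contains the primary-endpoint categories. The pooled SOC/PT tables are valid incidences of TEAEs as the SAP defines them; they are simply not on-drug incidences.

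It can also be said that withdrawal is assessed by DESS and PWC, both tabulated item by item (SAP 12.12 and 12.13), and that all AEs are listed. That stands: off-drug symptoms are not invisible, and no event disappears from the report. But DESS and PWC are fixed checklists of 43 and 20 items without seriousness or relatedness, and a listing is not an incidence table.

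A denominator of children actually followed off drug is a reasonable choice. That also stands, since dividing by all Safety subjects would understate off-drug incidence. The fault is tying the set to one clinic visit without applying the same set to the numerator.

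Finally, the amount of mismatch is uncertain. Protocol 11.4.11 lists only DESS at the two calls, and Table 2 marks no AE monitoring there, although Section 11.3.1 says that AEs are monitored by telephone. An SAE reported on days 15 to 30 for a child without EOS may not reach the CRF. These points limit the size but do not remove the problem, because SAE recording through 14 days is explicit.

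**Conclusion.** The concern holds in a bounded form. The post-treatment percentage in SAP 12.1 is not guaranteed to be a proportion of the group shown, and the SAP does not say whether events in children without a qualifying visit are counted or dropped. With the assumed counts above, the two readings differ by about 2 percentage points (7.6% against 5.7% at 80% attendance). The true difference depends on EOS attendance and on how many events come from children without the visit, neither of which the documents give. Separately, no planned table shows by term what arises on drug and what arises after stopping. Off-drug time is about 9% of the total for a completer and about 37% for a child stopping on Day 28. The overall on-treatment incidence is unaffected. The change is worth making before database lock, but it does not threaten the primary result.

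**What to change.** In SAP 12.1:

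1. Define the post-treatment at-risk set as Safety subjects with any scheduled follow-up contact (call 11E or 12E, late ET, or EOS) more than 3 days after last dose. Use it for both numerator and denominator. State that the calls count because Protocol 11.3.1 has AEs monitored there.
2. Report, by DB treatment group and overall, the number of Safety subjects with no such contact. List separately any post-treatment events in them, including SAEs and deaths. Do not admit a child to the set because an AE or SAE was recorded: anyone entering by that route alone has an event by definition, so the set would select on outcome.
3. Repeat the main SOC/PT tables (all TEAEs, serious TEAEs, maximum severity) for on-treatment and post-treatment onset, keeping the pooled tables as planned.

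The cost is SAP wording and a few extra tables, built from the onset split that the SAP already requires and from contact dates already collected. No new data are needed.
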